8.1 Screening (Optional) and Enrollment Visits

8.1.1 Visit 00, Screening (Day -28 to -1), Clinic Visit, All Treatment Arms, Optional

- Subjects will be provided with a description of this trial (purpose and study procedures) and asked to read and sign the ICF. The ICF will be signed prior to performing any study procedures, including administration of the first study vaccination.
- Demographic information will be obtained by interview of subjects.
- Eligibility criteria will be reviewed with subjects to ensure eligibility.
- Complete medical history will be obtained by interview of subjects to ensure eligibility.
- All concomitant medications taken within 60 days prior to signing the ICF will be reviewed with subjects to determine stability of chronic diseases and eligibility. Medications reported in the eCRF are limited to those taken within 30 days prior to the first study vaccination.
- Subject receipt of licensed, seasonal influenza vaccine over the current (2018-2019) and previous two influenza seasons (2016-2017 and 2017-2018), what type (inactivated or live attenuated) and approximate date of vaccination will be recorded on the appropriate DCF, if known. Prior receipt of licensed, seasonal influenza vaccine is not exclusionary, as long as it has been administered within the allowable window (see [Section 5.1.2](#)).
- Subject receipt of non-seasonal influenza vaccine, including those that are experimental, what type (inactivated or live attenuated), what subtype (e.g., A/H3, A/H5, A/H9) and approximate date of vaccination will be recorded on the appropriate DCF, if known. Prior receipt of non-seasonal influenza vaccine is not exclusionary, except influenza A/H7 vaccine (see [Section 5.1.2](#)).

- Vital signs, including oral temperature, pulse and BP, will be obtained to ensure eligibility. Subjects must not eat or drink anything hot or cold, or smoke within 10 minutes prior to taking oral temperature.
- Height and weight will be collected for the calculation of BMI.
- A physical examination will be performed on all subjects to include the following organs and organ systems: skin, head and neck, lungs, heart, liver, spleen, extremities, lymph nodes, and nervous system, and as an assessment for signs suggestive of PIMMCs, by a study clinician licensed to make medical diagnoses and listed on the Form FDA 1572 as the site PI or sub-investigator.

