8.3.2. HAI and Neut Regression Modeling

Regression modeling will be utilized to test for the effect of treatment variables i.e. prime boost combination (*PrimeBoost*), Boost dose (*BoostDose*), and interval between vaccinations (*Interval*), on immune response. Logistic regression will be fit for the seroconversion outcome. If the available titer data meet the required assumptions of normality after log transformation, multiple linear regression will be fit to log-transformed titers. Separate models will be fit for each assay (HAI, Neut), each strain (2013 A/H7N9, 2017 A/H7N9) and each time point (Day 22 post vaccination 1, Day 22 post vaccination 2, Day 181 post vaccination 2). All models will be fit with a similar structure for *PrimeBoost*, *BoostDose*, *Interval*, and covariates, for the PP population. The treatment variables will be defined as *PrimeBoost* (homologous, heterologous), *BoostDose* (3.75 mcg+AS03, 15 mcg), and *Interval* (21 days, 120 days). All models will be fit with and without adjustment for the following covariates (*Z*): age in years, sex (female, male), BMI (<30, ≥ 30), and prior receipt of seasonal influenza vaccine in the current season (did not receive 2018-2019 seasonal influenza vaccine, received 2018-2019 seasonal influenza vaccine) (did not receive 2016-2017 or 2017-2018 seasonal influenza vaccines, received 2016-2017 and/or 2017-2018 seasonal influenza vaccine). The models as shown below assume a linear relationship between age in years and both probability of seroconversion and GMT. The validity of this assumption will be assessed prior to analysis and, if the relationship between age and response is found to be non-linear, adjustments will be made to model parameters to satisfy regression assumptions. Modeling assumptions will be checked using standard diagnostic methods (e.g., using the INFLUENCE option in PROC LOGISTIC or PROC GLM). Parameter estimates and odds ratio estimates for the logistic models will be presented for the 2013 and 2017 A/H7N9 strains without covariate adjustment in Table 64, Table 65, Table 66, Table 67, and with covariate adjustment in Table 68, Table 69, Table 70, Table 71. Parameter estimates for the multiple linear regression models will be presented for the 2013 and 2017 A/H7N9s strain without covariate adjustment in Table 72, Table 73, Table 74, Table 75, and with covariate adjustment in Table 76, Table 77, Table 78, Table 79.

Model 1A: Logistic Regression (without covariate adjustment):

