$$\begin{aligned} \text{logit}[P(\text{seroconversion})] \\ = \beta_0 + \beta_1 \times \text{PrimeBoost} + \beta_2 \times \text{BoostDose} + \beta_3 \times \text{Interval} \\ + \beta_4 \times (\text{PrimeBoost} * \text{BoostDose}) + \beta_5 \times (\text{PrimeBoost} * \text{Interval}) + \varepsilon \end{aligned}$$

Model 1B: Logistic Regression (with covariate adjustment):

$$\begin{aligned} \text{logit}[P(\text{seroconversion})] &= \beta_0 + \beta_1 \times \text{PrimeBoost} + \beta_2 \times \text{BoostDose} + \beta_3 \times \text{Interval} \\ &+ \beta_4 \times (\text{PrimeBoost} * \text{BoostDose}) + \beta_5 \times (\text{PrimeBoost} * \text{Interval}) + \beta_6 \times Z + \varepsilon \end{aligned}$$

Model 2A: Multiple Linear Regression (without covariate adjustment):

$$\begin{aligned} \log(\text{titer}) &= \beta_0 + \beta_1 \times \text{PrimeBoost} + \beta_2 \times \text{BoostDose} + \beta_3 \times \text{Interval} \\ &+ \beta_4 \times (\text{PrimeBoost} * \text{BoostDose}) + \beta_5 \times (\text{PrimeBoost} * \text{Interval}) + \varepsilon \end{aligned}$$

Model 2B: Multiple Linear Regression (with covariate adjustment):

$$\begin{aligned} \log(\text{titer}) &= \beta_0 + \beta_1 \times \text{PrimeBoost} + \beta_2 \times \text{BoostDose} + \beta_3 \times \text{Interval} + \beta_4 \times (\text{PrimeBoost} * \text{BoostDose}) \\ &+ \beta_5 \times (\text{PrimeBoost} * \text{Interval}) + \beta_6 \times Z + \varepsilon \end{aligned}$$

Where Z is the matrix of covariates age, sex, BMI, and prior receipt of seasonal influenza vaccine as defined in Section 6.4. Subjects missing data for one or more covariates will be excluded from Models 1B and 2B.

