9.1. Demographic and Other Baseline Characteristics

Summaries of age, sex, ethnicity, race, BMI, and prior receipt of seasonal influenza vaccine will be presented by site ([Table 19](#), [Table 20](#)) and by study group ([Table 21](#), [Table 22](#)). Age will be summarized as a continuous variable. Ethnicity is categorized as Hispanic or Latino, or not Hispanic and not Latino. In accordance with NIH reporting policy, subjects may self-designate as belonging to more than one race or may refuse to identify a race, the latter reflected in the electronic case report form (eCRF) as “No” to each racial option. BMI will be summarized as a continuous as well as categorical variable, categorized as (<30, ≥30). Self-reported history of prior receipt of influenza vaccines will be broken down by the following categories: receipt of seasonal vaccines for prior seasons (2016-2017, 2017-2018), receipt of seasonal vaccine for the current season (2018-2019; considered up to receipt of study dose 2), and receipt of any A/H5 vaccines prior to enrollment. Demographic information for individual subjects will be provided in [Listing 6](#). Subjects’ prior influenza vaccination history (seasonal and non-seasonal) will be provided in [Listing 8](#).

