14.1.2 Demographic Data by Study Group

Table 19: Summary of Categorical Demographic and Baseline Characteristics by Site, All Enrolled Subjects

| Variable | Characteristic | [Site 1] (N=X) | | [Site 2] (N=X) | | [Site 3] (N=X) | | [Site 4] (N=X) | | [Site 5] (N=X) | | [Site 6] (N=X) | | All Subjects (N=X) | |
|--|---|-------------------|----|-------------------|----|-------------------|----|-------------------|----|-------------------|----|-------------------|----|--------------------------|----|
| | | n | % | n | % | n | % | n | % | n | % | n | % | n | % |
| Sex | Male | x | xx | x | xx | x | xx | x | xx | x | xx | x | xx | x | xx |
| | Female | | | | | | | | | | | | | | |
| BMI | < 30 | | | | | | | | | | | | | | |
| | ≥ 30 | | | | | | | | | | | | | | |
| Ethnicity | Not Hispanic or Latino | x | xx | x | xx | x | xx | x | xx | x | xx | x | xx | x | xx |
| | Hispanic or Latino | | | | | | | | | | | | | | |
| | Not Reported | | | | | | | | | | | | | | |
| | Unknown | | | | | | | | | | | | | | |
| Race | American Indian or Alaska Native | x | xx | x | xx | x | xx | x | xx | x | xx | x | xx | x | xx |
| | Asian | | | | | | | | | | | | | | |
| | Native Hawaiian or Other Pacific Islander | | | | | | | | | | | | | | |
| | Black or African American | | | | | | | | | | | | | | |
| | White | | | | | | | | | | | | | | |
| | Multi-Racial | | | | | | | | | | | | | | |
| | Unknown | | | | | | | | | | | | | | |
| Prior Seasonal Influenza Vaccination (Prior Seasons) | 2016-2017 Received | | | | | | | | | | | | | | |
| | 2016-2017 Not Received | | | | | | | | | | | | | | |

| Variable | Characteristic | [Site 1] (N=X) | | [Site 2] (N=X) | | [Site 3] (N=X) | | [Site 4] (N=X) | | [Site 5] (N=X) | | [Site 6] (N=X) | | All Subjects (N=X) | |
|--|---|-------------------|---|-------------------|---|-------------------|---|-------------------|---|-------------------|---|-------------------|---|--------------------------|---|
| | | n | % | n | % | n | % | n | % | n | % | n | % | n | % |
| | 2016-2017 Unknown | | | | | | | | | | | | | | |
| | 2017-2018 Received | | | | | | | | | | | | | | |
| | 2017-2018 Not Received | | | | | | | | | | | | | | |
| | 2017-2018 Unknown | | | | | | | | | | | | | | |
| Seasonal Influenza Vaccination (Current Season) | 2018-2019 Received | | | | | | | | | | | | | | |
| | 2018-2019 Not Received | | | | | | | | | | | | | | |
| | 2018-2019 Unknown | | | | | | | | | | | | | | |

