| | Unknown | | | | | | | | | | | | | | |
| Race | American Indian or Alaska Native | x | xx | x | xx | x | xx | x | xx | x | xx | x | xx | x | xx |
| | Asian | | | | | | | | | | | | | | |
| | Native Hawaiian or Other Pacific Islander | | | | | | | | | | | | | | |
| | Black or African American | | | | | | | | | | | | | | |
| | White | | | | | | | | | | | | | | |

| Variable | Characteristic | Group 1 2013 3.75+AS03/ 2017 3.75+AS03 (D1-D22) (N=X) | | Group 2 2013 3.75+AS03/ 2017 3.75+AS03 (D1-D121) (N=X) | | Group 3 2013 3.75+AS03/ 2017 15 (D1-D121) (N=X) | | Group 4 2017 3.75+AS03/ 2017 3.75+AS03 (D1-D22) (N=X) | | Group 5 2017 3.75+AS03/ 2017 3.75+AS03 (D1-D121) (N=X) | | Group 6 2017 3.75+AS03/ 2017 15 (D1-D121) (N=X) | | All Subjects (N=X) | |
|---|------------------------|---|---|--|---|--|---|---|---|--|---|--|---|--------------------------|---|
| | | n | % | n | % | n | % | n | % | n | % | n | % | n | % |
| | Multi-Racial | | | | | | | | | | | | | | |
| | Unknown | | | | | | | | | | | | | | |
| Prior Seasonal Influenza Vaccination (Prior Seasons) | 2016-2017 Received | | | | | | | | | | | | | | |
| | 2016-2017 Not Received | | | | | | | | | | | | | | |
| | 2016-2017 Unknown | | | | | | | | | | | | | | |
| | 2017-2018 Received | | | | | | | | | | | | | | |
| | 2017-2018 Not Received | | | | | | | | | | | | | | |
| | 2017-2018 Unknown | | | | | | | | | | | | | | |
| Seasonal Influenza Vaccination (Current Season) | 2018-2019 Received | | | | | | | | | | | | | | |
| | 2018-2019 Not Received | | | | | | | | | | | | | | |
| | 2018-2019 Unknown | | | | | | | | | | | | | | |

| Variable | Characteristic | Group 1 2013 3.75+AS03/ 2017 3.75+AS03 (D1-D22) (N=X) | | Group 2 2013 3.75+AS03/ 2017 3.75+AS03 (D1-D121) (N=X) | | Group 3 2013 3.75+AS03/ 2017 15 (D1-D121) (N=X) | | Group 4 2017 3.75+AS03/ 2017 3.75+AS03 (D1-D22) (N=X) | | Group 5 2017 3.75+AS03/ 2017 3.75+AS03 (D1-D121) (N=X) | | Group 6 2017 3.75+AS03/ 2017 15 (D1-D121) (N=X) | | All Subjects (N=X) | |
|---|---|---|---|--|---|--|---|---|---|--|---|--|---|--------------------------|---|
| | | n | % | n | % | n | % | n | % | n | % | n | % | n | % |
| Prior Receipt of H5 Influenza Vaccine | No Prior H5 Influenza Vaccinations | | | | | | | | | | | | | | |
| | Received Prior H5 Influenza Vaccinations | | | | | | | | | | | | | | |
| N= Number of subjects enrolled. | | | | | | | | | | | | | | | |

Table 22: Summary of Continuous Baseline Characteristics by Study Group, All Enrolled Subjects

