| Prime-boost | Homologous (reference) | - | - | - | - | - | - | - | - | - | - |
| | Heterologous | xxx.x | xxx.x | x.xxx | xx.x | xx.x-xx.x | xxx.x | xxx.x | x.xxx | xx.x | xx.x-xx.x |
| Boost Dose | 15 mcg (reference) | - | - | - | - | - | - | - | - | - | - |
| | 3.75 mcg + AS03 | xxx.x | xxx.x | x.xxx | xx.x | xx.x-xx.x | xxx.x | xxx.x | x.xxx | xx.x | xx.x-xx.x |
| Interval | 21 days (reference) | - | - | - | - | - | - | - | - | - | - |
| | 120 days | xxx.x | xxx.x | x.xxx | xx.x | xx.x-xx.x | xxx.x | xxx.x | x.xxx | xx.x | xx.x-xx.x |

n= XX (number of subjects with results available at 21 days post second study vaccination in the Per Protocol Population.)
XX subjects missing covariate data were excluded from this analysis.
SE = Standard Error.

Tables with similar format

Table 65: Logistic Regression Model to Evaluate the Relationship of Administration Schedule with HAI Seroconversion Against A/H7N9 Strains at 180 Days Post Second Study Vaccination, Per Protocol Population

Table 66: Logistic Regression Model to Evaluate the Relationship of Administration Schedule with Neut Seroconversion Against A/H7N9 Strains at 21 Days Post Second Study Vaccination, Per Protocol Population

Table 67: Logistic Regression Model to Evaluate the Relationship of Administration Schedule with Neut Seroconversion Against A/H7N9 Strains at 180 Days Post Second Study Vaccination, Per Protocol Population

Table 68: Logistic Regression Model to Evaluate the Relationship of Administration Schedule with HAI Seroconversion Against A/H7N9 Strains at 21 Days Post Second Study Vaccination, Adjusted for Baseline Covariates, Per Protocol Population (N=X)

| Model Parameter | Parameter Category | A/Shanghai/2/2013 (A/H7N9) | | | | | A/Hong Kong/125/2017 (A/H7N9) | | | | |
|--|---|----------------------------|-------|---------|------------|-----------|-------------------------------|-------|---------|------------|-----------|
| | | Parameter Estimate | SE | p-value | Odds Ratio | 95%CI | Parameter Estimate | SE | p-value | Odds Ratio | 95%CI |
| Intercept | N/A | xxx.x | xxx.x | x.xxx | - | - | xxx.x | xxx.x | x.xxx | - | - |
| Prime-boost | Homologous (reference) | - | - | - | - | - | - | - | - | - | - |
| | Heterologous | xxx.x | xxx.x | x.xxx | xx.x | xx.x-xx.x | xxx.x | xxx.x | x.xxx | xx.x | xx.x-xx.x |
| Boost Dose | 15 mcg (reference) | - | - | - | - | - | - | - | - | - | - |

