| | 3.75 mcg + AS03 | xxx.x | xxx.x | x.xxx | xx.x | xx.x-xx.x | xxx.x | xxx.x | x.xxx | xx.x | xx.x-xx.x |
| Interval | 21 days (reference) | - | - | - | - | - | - | - | - | - | - |
| | 120 days | xxx.x | xxx.x | x.xxx | xx.x | xx.x-xx.x | xxx.x | xxx.x | x.xxx | xx.x | xx.x-xx.x |
| Age (years) | N/A | xxx.x | xxx.x | x.xxx | xx.x | xx.x-xx.x | xxx.x | xxx.x | x.xxx | xx.x | xx.x-xx.x |
| Sex | Female (reference) | - | - | - | - | - | - | - | - | - | - |
| | Male | xxx.x | xxx.x | x.xxx | xx.x | xx.x-xx.x | xxx.x | xxx.x | x.xxx | xx.x | xx.x-xx.x |
| BMI | <30 (reference) | - | - | - | - | - | - | - | - | - | - |
| | ≥30 | xxx.x | xxx.x | x.xxx | xx.x | xx.x-xx.x | xxx.x | xxx.x | x.xxx | xx.x | xx.x-xx.x |
| Prior Receipt of Influenza Vaccine (Prior Seasons) | Did Not Receive 2016-2017 or 2017-2018 Seasonal Influenza Vaccination (reference) | - | - | - | - | - | - | - | - | - | - |
| | Received 2016-2017 and/or 2017-2018 Seasonal Influenza Vaccination | xxx.x | xxx.x | x.xxx | xx.x | xx.x-xx.x | xxx.x | xxx.x | x.xxx | xx.x | xx.x-xx.x |

| Model Parameter | Parameter Category | A/Shanghai/2/2013 (A/H7N9) | | | | | A/Hong Kong/125/2017 (A/H7N9) | | | | |
|--|--|----------------------------|-------|---------|------------|-----------|-------------------------------|-------|---------|------------|-----------|
| | | Parameter Estimate | SE | p-value | Odds Ratio | 95%CI | Parameter Estimate | SE | p-value | Odds Ratio | 95%CI |
| Receipt of Influenza Vaccine (Concurrent Season) | Did Not Receive 2018-2019 Seasonal Influenza Vaccine (reference) | - | - | - | - | - | - | - | - | - | - |
| | Received 2018-2019 Seasonal Influenza Vaccine (reference) | xxx.x | xxx.x | x.xxx | xx.x | xx.x-xx.x | xxx.x | xxx.x | x.xxx | xx.x | xx.x-xx.x |
| Prior Receipt of H5 Influenza Vaccine | No Prior H5 Influenza Vaccinations | - | - | - | - | - | - | - | - | - | - |
| | Received Prior H5 Influenza Vaccinations | xxx.x | xxx.x | x.xxx | xx.x | xx.x-xx.x | xxx.x | xxx.x | x.xxx | xx.x | xx.x-xx.x |

Note: Receipt of 2018-2019 vaccine is counted at any timepoint prior to receipt of the second study vaccination.
n= XX (number of subjects with results available at 21 days post second study vaccination in the Per Protocol Population).
XX subjects missing covariate data were excluded from this analysis.
SE = Standard Error.

Tables with similar format:

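### The shells for the unadjusted regression models exclude subjects for missing covariates, contrary to SAP 8.3.2; the adjusted models need a rule that keeps subjects with unclassifiable vaccine history

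*SAP*

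**What the plan says.** SAP 8.3.2 plans each regression in two versions: "All models will be fit with and without adjustment for the following covariates". The covariates are age, sex, BMI and two-level terms for seasonal influenza vaccine in the prior seasons and in 2018-2019. Models 1A and 2A, without covariates, report to Tables 64-67 and 72-75. Models 1B and 2B, with covariates, report to Tables 68-71 and 76-79. The missing-data rule names only the second pair: "Subjects missing data for one or more covariates will be excluded from Models 1B and 2B".

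The shells of Tables 64 and 72 show only an intercept, prime-boost, boost dose and interval, yet their footnotes read "XX subjects missing covariate data were excluded from this analysis". Tables 65-67 and 73-75 take the same format.

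Vaccine history is the covariate most open to being missing. SAP 9.1 describes it thus: "Self-reported history of prior receipt of influenza vaccines will be broken down by the following categories". Protocol 8.1.1 adds that type and "approximate date of vaccination will be recorded on the appropriate DCF, if known". The baseline shells (SAP Tables 19 and 21) have rows such as "2016-2017 Unknown" and "2018-2019 Unknown", but the model terms have no such level. SAP 6.5 imputes nothing and expects little missing data.

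**The concern.** Shells drive programming. With two conflicting instructions for the same eight tables, the result depends on which one the programmer follows:

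- If the footnote is followed, Models 1A and 2A lose subjects who have a titre and an assigned regimen, for want of a variable the model does not use. Precision falls for no return.
- If 8.3.2 is followed, Models 1A and 2A keep everyone and 1B and 2B do not. The adjusted and unadjusted estimates then differ partly because the subjects differ.

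These are alternatives and cannot both occur. Either matters because SAP 8.1 points to these models, and Section 8 otherwise plans only within-group summaries of HAI and neutralizing responses. The regressions are therefore the formal comparison between regimens. In 1B and 2B, a subject whose history fits neither level of a vaccine term has no place except exclusion.

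**Working it through.** **Text check**

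| Place | Models | Covariates in model? | Exclude for missing covariates? |
|---|---|---|---|
| SAP 8.3.2 | 1A, 2A | No | No |
| SAP 8.3.2 | 1B, 2B | Yes | Yes |
| Shells of Tables 64 and 72 (hence 65-67, 73-75) | 1A, 2A | No | Yes |
| Shells of Tables 68 and 76 (hence 69-71, 77-79) | 1B, 2B | Yes | Yes |
| Shell of Table 87 (solicited local events, same three treatment terms) | Safety model | No | No such footnote |

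The third row conflicts with the first. The same footnotes in Tables 64 and 72 also define n as per-protocol subjects with a result at the time point, with no requirement for complete covariates, so the shells conflict with themselves.

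Who counts as missing a covariate is also unsettled. Section 8.3.2 pairs 2016-2017 with 2017-2018 and adds 2018-2019. Section 6.4, to which 8.3.2 refers for the definition, pairs 2016-2017 with 2018-2019 and adds H5 vaccine. The adjusted shells also include an H5 term ("Received Prior H5 Influenza Vaccinations").

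**Reproducing the plan's own figure**

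The nearest stated figure is SAP Table 8 (protocol Table 14): 80% power with 27 per group, two-sided likelihood ratio test, alpha 0.05. The test statistic is G = 2 × Σ O × ln(O/E) over the four cells, compared with the 95th percentile of chi-square on 1 degree of freedom. Power is the sum of the two binomial probabilities over all outcomes that reject.

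- 0.10 v 0.42: 0.816
- 0.20 v 0.55: 0.794
- 0.30 v 0.68: 0.805
- 0.40 v 0.77: 0.813
- 0.50 v 0.84: 0.801

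All lie within two points of 80%, so the figure reproduces.

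**Effect of a further loss**

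The documents give no rate of unclassifiable history. The share lost below is an assumption. Group size is 27 × (1 − share), rounded down, which makes the figures slightly pessimistic.

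| Assumed share lost | n per group | Total | Exact power, range over the five rows |
|---|---|---|---|
| 0% | 27 | 162 | 0.79-0.82 |
| 2% | 26 | 156 | 0.78-0.81 |
| 5% | 25 | 150 | 0.76-0.82 |
| 10% | 24 | 144 | 0.74-0.80 |
| 20% | 21 | 126 | 0.68-0.70 |

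Individual rows do not fall smoothly, because the binomial is discrete. A two-group test is only a stand-in for the model's contrasts.

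Standard errors scale as 1/√(1 − share):

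- At 3%: 1/√0.97 = 1.015, with 0.03 × 162 ≈ 5 subjects lost.
- At 10%: 1/√0.90 = 1.054, with 0.10 × 162 ≈ 16 subjects lost.

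**How small item rates add up**

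If each of k vaccine-history items is unclassifiable in a proportion u, independently, the share excluded is 1 − (1 − u)^k.

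- u = 1%: 0.020 for two seasonal items (3.2 of 162), 0.030 with H5 (4.8).
- u = 5%: 0.098 for two (15.8 of 162), 0.143 with H5 (23.1).

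**The case against.** The strongest reply is that little may turn on this. SAP 6.5 expects minimal missing data, and the 'Unknown' rows may be placeholders. The SAP never says that 'Unknown' counts as missing, and in the protocol 'if known' follows a list of receipt, type and date, so it need not mean that receipt is often unknown. A prespecified complete-case rule with the excluded count footnoted is conventional. The footnote on the unadjusted shells may simply have been carried over. All of this stands, and it limits the size of the problem. It does not remove the contradiction. Nor do the documents say that 1A was deliberately matched to the subjects of 1B.

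A reader might infer two stronger things.

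- *That randomisation is broken.* An item missing before randomisation does not depend on the arm assigned, so excluding on it costs precision and narrows the population but does not by itself bias the comparison. Section 8.3.2 also already specifies the per-protocol population, grouped by vaccinations received.
- *That every subject with any unknown season is dropped.* The prior-season term is coded as receipt in either season, so one unknown season with the other received is still classifiable. Protocol 5.2.1 stratifies randomisation on 2017-2018 and/or 2018-2019 vaccine, so some classification was needed at enrolment. Later visits ask about non-study influenza vaccines.

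Two objections to a blanket 'Unknown' level also stand. The 2018-2019 term counts receipt up to dose 2, about 21 days after dose 1 in Groups 1 and 4 and about 120 days in the others. It is therefore partly post-randomisation, and the usual case for a missing-indicator level in baseline covariates does not fully cover it. The level may also be sparse: with 5 subjects and an assumed 80% seroconversion rate, all five respond with probability 0.8^5 = 0.33, and ordinary maximum likelihood then gives no finite coefficient.

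**Conclusion.** The shells for Tables 64-67 and 72-75 contradict SAP 8.3.2 and their own n. That conclusion needs no assumption. Taken literally, they remove analysable subjects from models without covariates and gain nothing by it.

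That unclassifiable vaccine history would be the main reason for exclusion from Models 1B and 2B is a reasonable inference from self-report, the 'Unknown' rows and the two-level terms. It is not stated. The size is unknown and could be zero. At an assumed 3% to 10%, the cost is 1.5% to 5.4% on standard errors; at 10%, two-group power falls from 0.79-0.82 to 0.74-0.80. If exploratory displays fall back to mITT under SAP 8.3, the proportional effect is the same.

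The models are labelled exploratory in a trial with no formal null hypothesis, and the primary mITT summaries are unaffected. What is at stake is precision and consistent analysis sets. It is still worth correcting before programming, because the first part costs nothing and the second very little.

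**What to change.** 1. Delete the covariate-exclusion footnote from Tables 64-67 and 72-75, so that Models 1A and 2A use every subject with a result in the analysis population.
2. In 8.3.2, replace the exclusion sentence for Models 1B and 2B with a rule that keeps subjects whose vaccine history is unclassifiable. Either use the randomisation stratum for prior seasonal vaccine (2017-2018 and/or 2018-2019, assigned at enrolment), or add an 'Unknown' level for history fixed at enrolment. If that level is too sparse for logistic regression, collapse it or use a penalised fit.
3. Say explicitly whether 'Unknown' counts as missing, and settle one covariate list across 6.4, 8.3.2 and the adjusted shells, including whether H5 vaccine belongs in it.

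The cost is SAP and shell wording, at most a few extra parameters and a possible sparse cell. If no history proves unclassifiable, deleting the footnote or adding an 'Unknown' level changes no estimate. Using the stratum would change the adjusted estimates somewhat, because it covers different seasons from the terms it replaces.
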